| Study Rationale | Single moxidectin doses of 8 mg, 16 mg and 32 mg will be evaluated in this study. Selection of the 8 mg starting dose was based on observations of mite mortality at exposures associated with this dose in protocol MDGH-MOX-2001. Two-fold increasing increments of 16 mg |

CONFIDENTIAL

| | |
|--|---|
| | 
and 32 mg will ensure sufficient separation in exposures between doses to support broad exploration of the exposure-response surface for the primary endpoint of Complete Cure. Single moxidectin doses up to 36 mg were well tolerated in patients aged 18 years and older with scabies in protocol MDGH-MOX-2001 and in healthy volunteers aged 18 years and older in two Phase 1 studies.
 
This study will compare each of the three moxidectin doses to placebo in outpatients aged 18 years and older with scabies without significant comorbidities to assess the efficacy of moxidectin in achieving Complete Cure by Day 28. A placebo control is included in this trial to establish background cure rates in the absence of clear untreated control data for the disease. There is no evidence from the literature to suggest that there are safety concerns for scabies patients who receive placebo, and standard of care will be available after the Day 28 assessments. All subjects regardless of treatment assignment may experience pruritus, so supportive therapies for symptom management such as unmedicated emollient creams and antihistamines will be allowed for subjects seeking relief from symptoms.
 
S. scabiei is highly contagious, and it is common for more than one member of a household to be infested. Because treatment efficacy could be affected by household members with an active but asymptomatic scabies infestation, all members of the household not enrolled in the study must receive treatment with permethrin 5% cream on the same day as the subject (index subject) receives their first dose of investigational product (IP) (Day 0). Only a single index subject from each household may be enrolled in the study.
 |
| Study Design: | Multi-country, multi-center, double-blind, parallel, randomized, placebo-controlled. |
| Number of Subjects: | Approximately 200 subjects. |
| Number of Centers: | This study will be conducted at approximately 8 to 20 sites internationally, including in the United States and Latin American region. |

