
CONFIDENTIAL

| | |
|---|---|
| | 
regardless of their randomized treatment group. Descriptive safety summaries for each treatment group and overall will be provided for treatment emergent adverse events, ECGs, laboratory parameters, and vital signs. Analyses for the safety data collected during the extended safety follow-up will also be conducted.
 
Details of the above analyses will be specified in the Statistical Analysis Plan (SAP).
 
Exploratory Pharmacokinetic Analyses
 
Twenty subjects from each of the cohorts will be randomly selected for sparse PK sampling (PK subset). Listings of individual moxidectin concentration versus time data by dose and mean (\pm standard deviation) moxidectin concentration versus time data by dose will be reported (tabular and/or figure format).
 |
| Special protocol requirement / issues: | 
If more than one household member is definitively diagnosed with scabies, the index subject is defined as the youngest eligible member of the household.
 
Household members 2 months of age and older and sexual contacts of all enrolled subjects must be treated with permethrin 5% cream on Day 0. Instructions for treatment administration of topical products and household cleaning will be provided orally and in writing.
 
All subjects enrolled in the study will have active management of their pruritus with provision of emollient and instructions to apply liberally and as often as is required.
 
Investigators should not enroll subjects who perceive their itch to be intolerable at Screening, for whom emollients and/or antihistamines is unlikely to provide relief, and/or who are at risk of not being able to complete the study because of intolerable pruritus.
 |

Table 1 Overall Schedule of Assessments

| Assessment | Screening (Day -7 to Day -1) | Day 0 In-clinic | | | | Day 7 By phone | Day 14 In-clinic | Day 28 In-clinic | Day 42 In-clinic | Week 12 By phone | Week 16 In-clinic |
|---|------------------------------------|--------------------|--------|-----------------|--------------|----------------------|---------------------|---------------------|---------------------|------------------------|----------------------|
| | | Pre- dose | Hour 0 | Hour 3 | Hour 10 | | | | | | |
| Visit window | N/A | N/A | N/A | ± 30 minutes | ± 2 hours | ± 1 day | ± 2 days | -2/+4 days | ± 2 days | ± 7 days | ± 7 days |
| Informed consent | X | | | | | | | | | | |

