S. scabiei is easily spread through close contact. Assessment of treatment efficacy could be confounded by household members with an active, even if asymptomatic, scabies infestation who cause reinfections in the enrolled index case. The signs and symptoms of scabies can reappear in as little as 24 hours in cases of reinfestation and would confound the interpretation of Day 28 Complete Cure rates if they occur during the study. Limited data is available to quantify the risk of infection from household members or vice versa, but it is accepted that the risk is not zero. Presumptive treatment of household members is a conservative strategy to minimize the risk of reinfection of enrolled subjects across all the treatment arms and is a consistent approach with many available guidelines for the treatment of scabies, including those from the Centers for Disease Control and Prevention²⁶, which recommends that the close personal contacts of scabies patients should also be treated at the same time to prevent reinfestation of the patient and/or infestation of the contacts. Permethrin 5% cream has been selected to standardize the treatment of household members as it is a widely approved product in broad use for this population, and unlike ivermectin 200 µg/kg, can be used in infants 2 months of age and older.

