12. Known or suspected hypersensitivity to macrocyclic lactones or excipients used in the formulation of moxidectin or ivermectin.
13. Known or suspected hypersensitivity to any of the components in permethrin 5% cream, to any synthetic pyrethroid or pyrethrin, or to the components of spinosad 0.9% topical suspension.
14. Known, suspected or at risk of *Loa loa* coinfection.
15. Difficulty swallowing tablets or capsules.
16. Pregnant or breastfeeding or planning to become pregnant from Screening until 16 weeks after treatment with IP.
17. Known or suspected alcohol or illicit substance abuse.
18. Unwilling, unlikely or unable to comply with all protocol specified assessments.
19. Previous enrolment in this study.
20. Previous moxidectin exposure within 6 months (5-half-lives) from Baseline.
21. Has household members who refuse or are unable to receive permethrin 5% cream treatment for scabies.

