8.5 Special Protocol Issues

8.5.1 Treatment of Contacts

S. scabiei is highly contagious, and it is common for more than one member of a household to be infested. Because Complete Cure rates could be affected by household members with an active but asymptomatic scabies infestation, all members of the household must receive treatment with permethrin 5% cream on the same day that the index subject receives their dose of IP. Instructions for treatment administration of permethrin should be provided by the clinical staff orally and in writing, and household members will be asked to confirm when the treatment is administered.

The index subject must be counselled to avoid contact with any treatments taken by their close personal contacts.

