9.6 Protocol Deviations

A blinded review of protocol deviations documented during the study will be completed prior to the database freeze/lock and blind break for the Day 42 analysis. Protocol deviations are categorized at the time of entry into the Protocol Deviation eCRF page, but categorization will be reviewed during blinded review of all protocol deviations, and they will also be classified as major/minor:

- Consent procedures
- Inclusion/exclusion criteria
- Randomization procedures

- Concomitant medication/therapy
- Study procedures
- Serious adverse event (SAE) reporting
- Dosing
- Unblinding
- Scabies Assessment outside the Day 28 Visit Window
- Other Visit schedule/ interval
- COVID-19 related
- Other

Major protocol deviations will be defined as deviations that could potentially have a meaningful impact on the efficacy or safety results. Subjects with major protocol deviations that might impact efficacy will be excluded from the PPAS.

Some categories of major protocol deviations that might be considered as having a meaningful impact on the efficacy results include but are not limited to:

- Subjects failing any eligibility criteria,
- Subjects with treatment administration errors,
- Subjects randomized but not exposed to study drug (exclusion from FAS, PPAS, SfAS), and PK,
- Significant non-compliance with specified study visits windows,
- Administration of scabicides prior to the Day 28 visit (note: the exposure to scabicides prior to Day 28 is considered a major protocol deviation and subjects will be considered non-responders for the primary analysis)

Protocol deviations leading to missing data will also be reviewed to assess the reasons why the data are missing and whether they are considered informative or non-informative reasons for the purposes of handling of missing data described in Section 9.11.2. Where the reason(s) for missing data is unknown and/or not fully documented, the default will be to assume informative missing. Examples of non-informative missing data might be:

- Missed visit due to weather, travel, or childcare,
- Missed visit due to COVID-19 or COVID-19 exposure,
- Missed assessment due to equipment failure.

All determinations of informative and non-informative missing data will be fully documented and reported.

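### The protocol gives two conflicting rules on which contacts must receive permethrin, and exclusion 21 does not settle how a household with an infant under 2 months is classed

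*Protocol*

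**What the plan says.** Contact treatment is described in four places.

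- **Synopsis, special protocol requirements:** "Household members 2 months of age and older and sexual contacts of all enrolled subjects must be treated with permethrin 5% cream" on Day 0. Elsewhere the synopsis names this section as the place for details of family treatment.
- **Synopsis, Study Rationale:** "all members of the household not enrolled in the study must receive treatment with permethrin 5% cream on the same day as the subject" is first dosed. It has no age limit and does not mention sexual contacts.
- **Section 8.5.1:** "all members of the household must receive treatment with permethrin 5% cream on the same day that the index subject receives their dose of IP". Again there is no age limit and no mention of sexual contacts. Household members are asked to confirm when they have been treated.
- **Exclusion 21, Section 8.3 and synopsis, identical wording:** a subject is excluded who "Has household members who refuse or are unable to receive permethrin 5% cream treatment for scabies".

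Section 5.4.3 gives the reason for the measure. Infested household members could reinfest the index subject, and that would confound Day 28 Complete Cure. It says the risk cannot be well quantified but is not zero. It gives usability from 2 months of age as one reason for choosing permethrin, and it cites guidance that "close personal contacts of scabies patients should also be treated at the same time".

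**The concern.** A site cannot follow all of these texts at once. For a sexual contact outside the household, one text requires treatment and the others are silent. For an infant under 2 months, two texts require treatment and one does not, while Section 5.4.3 describes the product as usable only from that age. The same infant raises an eligibility question, because exclusion 21 does not say whether a member below the age limit counts as *unable*.

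The matter bears on the primary endpoint. Under SAP 6.1, a single lesion or any pruritus at Day 28 means the subject is not a Complete Cure, so reinfestation from an untreated contact would turn a cured subject into a failure. The planned power is only about 75% per comparison, which leaves little reserve.

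**Working it through.** **Step 1. Compare the texts.**

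| Place | Household members | Lower age limit | Sexual contacts | Role |
|---|---|---|---|---|
| Synopsis, special requirements | yes | 2 months | yes | who is treated |
| Synopsis, Study Rationale | all not enrolled | none | not mentioned | who is treated |
| Section 8.5.1 | all | none | not mentioned | who is treated |
| Exclusion 21 (8.3 and synopsis) | those who refuse or are unable | none | not mentioned | who is enrolled |

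There are two contact sets. The special requirements stand alone on one side. The conflict is not simply synopsis against body, because the synopsis also contradicts itself. We found no statement of which text prevails.

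**Step 2. Work through two cases.**

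- *Infant under 2 months at home.* Section 8.5.1 requires treatment and the special requirements do not. If the infant is read as unable to receive permethrin, exclusion 21 excludes the subject. If a site takes the special requirements to mean that no treatment is needed, it could enrol the subject. Both treatment and enrolment can differ.
- *Sexual contact living elsewhere who refuses.* The special requirements cannot be met. No version of the criteria excludes the subject on this ground. Treatment can differ; formal eligibility does not.

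**Step 3. Reproduce the planned power.** Inputs from Protocol 15.2.1 and SAP 4: n = 50 per arm, 40% versus 70%, pooled-variance Z-test, two-tailed alpha 0.019, hence z = 2.3455.

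Power = Φ[(d − z·s0)/s1], where d is the rate difference, s0 = √(2p̄(1−p̄)/n) and s1 = √(p0(1−p0)/n + p1(1−p1)/n).

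- p̄ = 0.55, s0 = 0.0995, s1 = 0.0949
- (0.30 − 2.3455 × 0.0995)/0.0949 ≈ 0.702, so power = 75.9%

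This agrees with the stated 75%. The large-sample Dunnett critical value for three comparisons with one control is 2.349, or alpha 0.0188, which rounds to the stated 0.019.

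**Step 4. Illustrate the direction.** The documents give no reinfestation rate. Assume that a share r of otherwise cured subjects in every arm is reinfested before Day 28, so the rates become 0.40(1−r) and 0.70(1−r).

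| r (assumed) | Placebo | Moxidectin | Difference | Power |
|---|---|---|---|---|
| 0% | 40.0% | 70.0% | 30.0 points | 75.9% |
| 1% | 39.6% | 69.3% | 29.7 points | 74.7% |
| 5% | 38.0% | 66.5% | 28.5 points | 70.2% |
| 10% | 36.0% | 63.0% | 27.0 points | 64.4% |

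Here r applies to all cured subjects. The mismatch exposes only those with an infant under 2 months at home or an untreated sexual contact outside the household. The higher rows therefore show direction and are not a forecast.

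**The case against.** The best defence is that this is a wording slip with little practical reach, and much of that stands.

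- **The eligibility criterion is the same everywhere.** Exclusion 21 reads identically in synopsis and body. A reader might infer that a subject with a young infant is eligible under the synopsis but not under the body. The documents do not support that: the special requirements state who is treated and are not an eligibility criterion. What remains is uncertainty over the word *unable*.
- **The infant case is narrow.** Breastfeeding women are already excluded by criterion 16.
- **The sexual-contact difference does not change who is enrolled.** Exclusion 8 also lets the investigator exclude for a circumstance that would confound evaluation. Section 5.4.3 names household members as the confounding source; wider contacts enter through the cited guidance and the general statement about reinfestation.
- **Safeguards exist.** Section 8.5.1 asks household members for confirmation, and Section 9.3.2 requires eligibility to be confirmed before randomization. SAP 9.6 introduces its list as "Some categories of major protocol deviations that might be considered as having a meaningful impact on the efficacy results", includes eligibility failures, and says the list is not exhaustive. It does not name a contact who agreed but was not treated, or an untreated sexual contact.

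A reader might also infer that reinfestation would hurt only the moxidectin arms, because those subjects are cleared of mites. On that assumption power would be about 63% at 5% and 48% at 10%. The documents do not support it. The plan assumes that 40% of placebo subjects are also cured, and they could be reinfested too. Moxidectin's half-life of roughly 20 to 47 days (5.3.2.1), with its persistence in skin in the porcine model (5.4.1), could even give treated subjects some protection.

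None of this removes the contradiction about who must be treated.

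**Conclusion.** The point holds as a contradiction between operative instructions. The synopsis special requirements, the designated place for family-treatment details, name one contact set; the Study Rationale and Section 8.5.1 name another; exclusion 21 screens household members only. Sites could treat different contacts and could class households with an infant under 2 months differently.

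The expected consequence is attenuation and some loss of power. Randomization within region should spread the exposure over the arms, so the documents give no ground for expecting bias in favour of moxidectin. The loss cannot be sized from the documents. Under the equal-proportion assumption it is about 1.2 percentage points of power at 1% reinfestation (75.9 − 74.7, from unrounded values 1.1) and 5.7 points at 5% (75.9 − 70.2). The first is nearer to what a narrow gap might produce, but neither rate is an estimate. The reason to act is that the instructions conflict on a matter the protocol itself calls confounding, and that correction is nearly free.

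**What to change.** Reconcile the synopsis special requirements, the synopsis Study Rationale, Section 8.5.1 and both copies of exclusion 21 so that they name one contact set. State how a household with a member under 2 months is classed for eligibility, and whether exclusion 21 is meant to screen the whole contact set or household members only. Which contacts are to be treated is for the sponsor's clinicians, and this review takes no position on it.

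Two additions are optional. Record on the CRF the confirmation that Section 8.5.1 already requests; the Day 0 procedures and Table 1 have no entry for it. Name a required contact not treated on Day 0 among the examples in SAP 9.6, for the blinded deviation review. The latter affects only the per-protocol sensitivity analysis. The primary analysis uses the FAS, so it would not recover any lost power.

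The cost is a wording clarification, one CRF item if adopted, and possibly a few more screen failures.

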8.4 Other Study Eligibility Criteria Considerations

To assess any potential impact on subject eligibility with regards to safety, the Investigator must refer to the relevant document(s) for detailed information regarding warnings, precautions, contraindications, AEs, and other significant data pertaining to the IP being used in this study. Such documents may include the IB.

8.4.1 Contraception

As no adequate and well-controlled studies of moxidectin in pregnant women have been conducted, the safety of moxidectin in pregnancy has not been established. All women of child-bearing potential (WOCBP) (defined as sexually mature women who have had menses within the preceding 24 months and have not undergone hysterectomy, bilateral oophorectomy or tubal ligation) must have a negative pregnancy test at Screening. Serum pregnancy testing will be performed at Screening and repeated (urine test) pre-dosing if Baseline (Day 0) is more than 24 hours later and at Week 16 or at the End of Study visit, whichever occurs earlier.

WOCBP must agree not to attempt to become pregnant during the study until 16 weeks following IP administration. If participating in sexual activity that could lead to pregnancy, then WOCBP must agree to use a highly effective method of contraception during the study until 16 weeks following IP administration. Highly effective methods of contraception are defined as

CONFIDENTIAL

those methods that have a failure rate of less than 1% per year when used consistently and correctly. These methods include combined (estrogen and progestogen containing) hormonal contraception associated with inhibition of ovulation; progestogen-only hormonal contraception associated with inhibition of ovulation; intrauterine devices; implantable rod; male partner who has undergone successful surgical sterilization; or abstinence as the subject's usual and preferred lifestyle.

Additional precaution is warranted for hormonal contraceptives that are sensitive CYP3A4 substrates as the clinical risk of CYP3A4 induction by moxidectin at doses higher than 8 mg is unknown. Barrier methods of contraception, such as diaphragms with spermicide or male condoms, should be used by subjects on hormonal contraception or if contraception is started within 7 days of IP administration for a minimum of 14 days after.

Women who are not of reproductive potential (who have been postmenopausal for at least 24 consecutive months or have undergone hysterectomy, bilateral oophorectomy or tubal ligation) are not required to use contraception.

8.4.2 Retesting and Rescreening

Subjects who have not been randomized and are determined to be ineligible due to unexpected laboratory, ECG, and/or vital signs abnormalities may have the relevant parameter(s) repeated once only. Otherwise, rescreening is not permitted.

8.5 Special Protocol Issues

8.5.1 Treatment of Contacts

S. scabiei is highly contagious, and it is common for more than one member of a household to be infested. Because Complete Cure rates could be affected by household members with an active but asymptomatic scabies infestation, all members of the household must receive treatment with permethrin 5% cream on the same day that the index subject receives their dose of IP. Instructions for treatment administration of permethrin should be provided by the clinical staff orally and in writing, and household members will be asked to confirm when the treatment is administered.

The index subject must be counselled to avoid contact with any treatments taken by their close personal contacts.

8.5.2 Pruritus

Scabies has a widely variable clinical presentation, ranging from mild disease with few scabies mites and few visible skin changes, to crusted scabies. Pruritus is the most commonly occurring symptom of scabies, but does not occur with the same intensity in all patients. Although some patients may report intense pruritus, several studies show the majority report pruritus as having mild to moderate intensity. Importantly from both the patient management perspective and measurement of trial outcomes, pruritus is known to have a subjective component and is vulnerable to confounding factors such as mood, environmental factors and stress.

All subjects enrolled in the study will have active management of their pruritus with provision of emollient and instructions to apply liberally and as often as is required.

Investigators should not enroll subjects who perceive their itch to be intolerable at Screening, for whom emollients and/or antihistamines is unlikely to provide relief, and/or who are at risk of not being able to complete the study because of intolerable pruritus.

9 SCHEDULE OF ASSESSMENTS AND PROCEDURES

9.1 Study Schedule of Evaluations

The schedule of assessments is presented in [Table 1](#).

